**Research Methods**

**2.0 Design**

In a parallel cluster randomized trial, we will randomize 8 VA facilities to implement the EQUIPPED QI intervention with either passive provider feedback (4 sites) or active provider feedback (4 sites). Specifically, it is anticipated that all sites will implement EQUIPPED components including: didactic education concerning the Beers Criteria; decision support by order sets; and monthly provider prescribing feedback. However, *passive* provider feedback sites will implement monthly provider feedback via an electronic dashboard with audit, feedback and peer benchmarking, while *active* provider feedback sites will implement one-to-one (1:1) in-person academic detailing from a professional colleague that includes in-person audit, feedback, and peer benchmarking and provide on-site expertise. To compare the effectiveness of EQUIPPED with in-person academic detailing including proactive feedback (*active feedback*) versus EQUIPPED with passive electronic audit and feedback (*passive feedback*) intervention, we will evaluate the monthly proportion of PIM prescribing as % of individual prescriptions (primary outcome) in each arm. It is hypothesized that the decline in PIM rates will be greater in the presence of EQUIPPED with active feedback compared to EQUIPPED with passive feedback.

After the initial recruitment and randomization, one of the eight sites had to pause order set development due to COVID-19 and an off-site detail of one of the core implementation team members. After several months of stalled progress with EQUIPPED implementation, the site decided to pause EQUIPPED implementation until at least spring 2021. We have recruited an additional site to fill the open study spot. We will continue to collect prescribing data from both sites and collect implementation evaluation data from the newly recruited facility based on the timeline for the award. If the initial facility determines they can move forward in 2021, we propose collecting implementation evaluation data as originally planned (would increase number of sites to n=9). The data analysis plan for this change is reflected below in section 2. 1. 3.

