### 2.1.3 Aim 1 Data Analysis Plan

The statistical analysis plan described below may be adjusted based on changes in statistical science methods and/or to fit the specific mathematical properties of collected data.

The primary efficacy outcome of interest is the % of prescriptions that are PIMS as defined according to the Beers criteria prescribed to adults aged 65 and older and discharged from the ED. Poisson regression will be used to evaluate the number of PIMs prescribed for 6 months prior to the first EQUIPPED intervention at each site compared to at least 12 months of prescribing data following the implementation of EQUIPPED provider feedback at the local site. The total number of prescriptions will be used as an offset term to account for differing volumes of prescriptions between sites as well as potentially over time. We will not have a single date of implementation as the implementation period will begin based on local scheduling. The implementation timeline will vary by site. Poisson regression will be used to evaluate the effect of the two methods of provider feedback on prescribing behavior of PIMs by including randomization group as a variable in the model. If the Poisson model demonstrates over (or under) dispersion other, related, models will be explored, e.g., negative binomial. Analyses will be conducted using SAS version 9.4 (SAS Institute, Cary, NC). Our primary aim, on which we will base sample size, is the evaluation of the EQUIPPED implementation. We will have 6 months of pre- and 12 months of post data including hospital site, provider ID, total prescriptions, and PIMs.

We will conduct three analyses for the primary outcome of monthly PIM prescribing to assess the impact of both the initially recruited, randomized sites and the newly recruited VA facility's inclusion. The analyses will be conducted as follows:

- 1) Intention to treat analysis: Include eight originally randomized sites

- 2) Per protocol analysis: Include seven originally randomized sites that implemented EQUIPPED
- 3) Per protocol analysis: Include seven originally randomized sites that implemented EQUIPPED + the non-randomized 8th site that was added to the Active Provider feedback EQUIPPED group

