#### 2.1.4 Sample Size and Power Considerations (power calculated prior to trial) and Selection/Recruitment of Sites/Subjects

Power estimates are based on Aim 1, hypothesis 1 (i.e., primary outcome of change). The primary outcome is at the level of the individual prescribing decision. We plan to engage a total of eight VA sites with at least 1,200 eligible prescriptions per year to patients ages 65+ per ED. This will provide a total of approximately 4,800 eligible prescriptions during the pre-implementation period and 9,600 eligible prescriptions during the post time period. It can be reasonably assumed that these eligible prescriptions will be equally distributed between the randomization groups. Based upon preliminary data, we estimate that approximately 7.1% of these total prescriptions at baseline will be Beers PIMS. Given this sample size, we have near 100% power to detect a change in the risk of PIMs of 5% (i.e., 7.1% to 2.1%).

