Aim 1 Data Analysis Plan: The primary efficacy outcome of interest is the % of prescriptions that are PIMS as defined according to the Beers criteria prescribed to adults aged 65 and older and discharged from the ED. Poisson regression will be used to evaluate the number of PIMs prescribed for 6 months prior to the first EQUIPPED intervention at each site compared to at least 12 months of prescribing data following the implementation of EQUIPPED provider feedback at the local site. The total number of prescriptions will be used as an offset term to account for differing volumes of prescriptions between sites (Table 1) as well as potentially over time. We will not have a single date of implementation as the implementation period will begin based on local scheduling. The implementation timeline will vary by site. Poisson regression will be used to evaluate the effect of the two methods of provider feedback on prescribing behavior of PIMs by including randomization group as a variable in the model. If the Poisson model demonstrates over (or under) dispersion other, related, models will be explored, e.g., negative binomial. Analyses will be conducted using SAS version 9.4 (SAS Institute, Cary, NC). Our primary aim, on which we will base sample size, is the evaluation of the EQUIPPED implementation. We will have 6 months of pre- and 12-months of post data including hospital site, provider ID, total prescriptions, and PIMs.

Sample Size and Power Considerations

Power estimates are based on **Aim 1**, hypothesis 1 (i.e., primary outcome of change). The primary outcome is at the level of the individual prescribing decision. We plan to engage a total of eight VA sites with at least 1,200 eligible prescriptions per year to patients ages 65+ per ED. This will provide a total of approximately 4,800 eligible prescriptions during the pre-implementation period and 9,600 eligible prescriptions during the post time period. It can be reasonably assumed that these eligible prescriptions will be equally distributed between the randomization groups. Based upon the data presented in table 1, we estimate that approximately 7.1% of these total prescriptions at baseline will be Beers PIMS. Given this sample size, we have near 100% power to detect an absolute change in the risk of PIMs of 5% (i.e., 7.1% to 2.1%).

Table 1. Characteristics of First Three Recruited Sites (FY16 data)

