Although the primary trial outcome is at the level of the individual prescription/provider decision, 8 participating sites will be randomized to either EQUIPPED with passive provider feedback or EQUIPPED with active provider feedback. Randomization is occurring at the facility level because the components of the decision support are made available to all ED providers at a given facility. It is not feasible to make them available to only a subset of providers or provider decisions at a given facility. To ensure relative balance of facility size across arms, randomization will be stratified based on the percentage of prescriptions written in the ED for patients age 65+ in the ED during the 6 full months prior to randomization. One stratum will include the 4 selected sites with the highest percentage with the 4 remaining facilities in the second stratum.

4. Plans for an specification of the purpose of any interim analysis

Aims 1 and 3: We do not have interim analyses planned for the prescribing data analysis or the health economics analysis.

Aim 2: Formative Data Analysis. Core to the concept of formative evaluation is continual analysis of results and feedback to stakeholders. Key data sources are qualitative interviews, surveys to assess organizational readiness for change, and collection of detail about organizational characteristics and implementation process and progress. All qualitative interviews will be transcribed in full. Rapid analysis approaches will generate preliminary findings to share among the research team. This effort will involve an initial review of factors identified as directly impacting the process of supporting implementation and impact on clinical workflow. Rapid analysis will be followed by in-depth content analysis. Content analysis to examine the telephone interviews will involve three phases: data coding, within-case analysis, and between-case analysis. In the data coding phase, we will use qualitative data analysis software (ATLAS.ti) to code the study data. The OTIE will provide a starting list of codes, which we will supplement with emergent codes as analysis proceeds. Using a common codebook, two investigators will conduct a preliminary test of codes by independently coding five transcripts. Based on the preliminary test, the investigators will sharpen the coding manual's definitions, decision rules, and examples. Research assistants will code the remaining documents.

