Aim 2: The formative analysis could be impacted by two types of dropouts: individual (provider) dropout and cluster (facility) dropout. Individual dropout could occur if providers fail to complete follow-up surveys. If this occurs, we will use the data we have collected to that point. All surveys will occur via email and will be brief (20 minutes or less). Providers will receive up to 5 email reminders to complete surveys. Facility dropouts could occur for various reasons, e.g. if the respective facility is not ready to implement EQUIPPED or leadership refuses to participate. We will minimize dropouts by working closely with the facility EQUIPPED champion to define the needed resources prior to the site's commitment to participate. During the implementation period, the team at the Atlanta site of the Birmingham/Atlanta GRECC will conduct bi-weekly conference calls for the site champions to discuss the team's local implementation strategy and identify strategies to address challenges. Separate calls will be held for sites randomized to passive feedback versus active feedback EQUIPPED to prevent influencing the provider feedback process at passive feedback sites. During calls, the site champions will have time to review cases, ask questions, and receive advice from the implementation team and other site leads. The EQUIPPED team has experience conducting similar calls nationally for the current VA sites since 2013.

Aim 3: The analysis will be based on data from available time logs from each facility. Our team has extensive experience using time logs with clinicians. While we will seek to collect time logs from each facility, the time for collected thought the logs will be averaged across logs/facilities, reducing the impact of any missing data from time logs. Other information is based on generally available national information on salaries by position type (not any information from individual people).

6. Definitions of covariates to be included in adjustment models

Aim 1: We will include stratum (high vs. low prescriber of PIMs at the facility level) and randomization group (active vs. passive feedback).

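### Eight sites are randomised, but the Aim 1 Poisson model has no site effect, so the active versus passive comparison treats prescriptions as independent and rejects a true null too often

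*Protocol*

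**What the plan says.** Both documents call the study a parallel cluster randomised trial of eight facilities, and Protocol 2.0 puts four in each arm. SAP section 3 recognises that allocation and outcome sit at different levels: "Although the primary trial outcome is at the level of the individual prescription/provider decision, 8 participating sites will be randomized". Protocol 2.1.4 restates the outcome level: "The primary outcome is at the level of the individual prescribing decision".

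The Aim 1 model, in the same words in Protocol 2.1.3 and SAP section 1, is a Poisson regression for the number of PIMs. The feedback modes are compared "by including randomization group as a variable in the model". On volume, the plan says "The total number of prescriptions will be used as an offset term to account for differing volumes of prescriptions between sites". SAP section 6 gives the Aim 1 covariates: "We will include stratum (high vs. low prescriber of PIMs at the facility level) and randomization group (active vs. passive feedback". If the model fits badly, "If the Poisson model demonstrates over (or under) dispersion other, related, models will be explored, e.g., negative binomial".

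The site identifier will be available: "We will have 6 months of pre- and 12 months of post data including hospital site, provider ID, total prescriptions, and PIMs". It is listed as a data field and never as a model term.

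**The concern.** A site's arm does not change, so all information on active versus passive comes from comparing four sites with four others. Prescriptions from one emergency department share prescribers, formulary, case mix and implementation effort. A model without a site term takes its standard error from the prescription count, and that standard error shrinks as volume grows while the number of independent units stays at eight.

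The offset scales for volume and does nothing about correlation. Negative binomial adds variance record by record but leaves records from one site independent. Ordinary differences between sites, in PIM level or in how much they improve, could therefore be reported as an effect of the feedback mode. The same model serves the intention-to-treat set and both per-protocol sets, one of which has only seven sites.

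**Working it through.** **1. The plan's own figure.** Protocol 2.1.4 claims near 100% power for 7.1% to 2.1% with 4,800 pre and 9,600 post prescriptions. With independent prescriptions, SE = √(0.071×0.929/4,800 + 0.021×0.979/9,600) = 0.0040, so z = 0.05/0.0040 ≈ 12.5 and power exceeds 0.9999. For two arms of 4,800 post prescriptions, SE = 0.0042 and z ≈ 11.8. The stated figure is reproduced with no allowance for clustering.

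**2. Site variation.** SAP Table 1 counts give 461/7,756 = 5.94%, 545/7,164 = 7.61% and 1,345/18,868 = 7.13%: SD 0.86 points, relative SD 0.12, SD of log rates 0.13. (The printed percentages for two rows are interchanged, which barely alters the SD.) Mean volume is 33,788/3 = 11,263 per year, about 940 per month. No figure is given for site-to-site variation in the *change*, so the SD of the log change, τ, is an assumption, taken from 0 to 0.3.

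**3. Design effect, arm comparison of rates.** ICC = SD²/[p(1−p)] = 0.0086²/(0.071×0.929) = 0.0011. With 1,200 prescriptions per site, DE = 1 + 1,199×0.00112 = 2.34. The false-positive rate is 2[1 − Φ(1.96/√2.34)] = 20%. With 11,263 per site, DE = 13.6 and the rate is 60%.

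**4. Simulation at 100 prescriptions per site-month.** Four sites per arm, 6 pre and 12 post months, rate 7.1% halved after implementation in both arms, no arm effect, stratum in the Poisson models, two-sided 5%, 1,000 runs per row. Entries are % rejected.

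| Relative site SD | τ | Group, post data | Group, all data | Arm-by-period | Arm-by-period, dispersion-scaled | Negative binomial, group, post data | t-test on 8 site log changes |
|---|---|---|---|---|---|---|---|
| 0 | 0 | 4.5 | 4.9 | 4.8 | 4.1 | 4.0 | 5.3 |
| 0.12 | 0 | 11.1 | 15.1 | 4.7 | 4.1 | 10.1 | 3.3 |
| 0.20 | 0 | 22.3 | 31.1 | 4.4 | 3.2 | 21.1 | 4.3 |
| 0.12 | 0.1 | 20.6 | 23.0 | 7.1 | 6.3 | 18.7 | 4.5 |
| 0.12 | 0.2 | 27.6 | 27.6 | 15.5 | 13.3 | 25.5 | 5.1 |
| 0.20 | 0.2 | 34.7 | 41.8 | 14.7 | 11.4 | 30.8 | 4.7 |
| 0.20 | 0.3 | 46.9 | 44.9 | 27.5 | 21.5 | 40.8 | 4.3 |

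Without site variation every test is close to 5%. With it, negative binomial gives 10-41%, so the fallback does not repair the problem.

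**5. Larger volumes, arm-by-period.** With m prescriptions per site-month, expected PIMs per site are n₀ = 6m×0.071 before and n₁ = 12m×0.071×0.5 after. The model's variance is V = ½(1/n₀ + 1/n₁), the true variance is V + ½τ², and the false-positive rate is 2[1 − Φ(1.96√(V/(V + ½τ²)))]. For m = 940 and τ = 0.1, n₀ = n₁ = 400, V = 0.0025, true variance 0.0075, rate 26%.

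| m | τ = 0 | τ = 0.1 | τ = 0.2 |
|---|---|---|---|
| 100 | 5% | 7.5% | 15% |
| 600 | 5% | 19% | 43% |
| 940 | 5% | 26% | 51% |

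Separate simulations with a common 40% decline and site SD 0.13 agree. At 940 per month arm-by-period gives about 5%, 27% and 54% for τ = 0, 0.1 and 0.2, and the group main effect on pre and post data gives 63%, 64% and 70%. The t-test on site-level log changes stays at 4.5-5.0%. Scaling for over-dispersion at these volumes still leaves 16-41% for arm-by-period.

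**The case against.** The strongest reply is that the hypothesis concerns a greater *decline* and the endpoint is reduction from baseline. That is an arm-by-period contrast, in which stable site differences cancel. If sites do not differ in how much they change, its error rate is about 5% at any volume; at minimum volume with τ = 0.1 it is only 7-8%. This is correct, and it means the highest rates apply to a pooled group effect that does not test the stated hypothesis. But neither document states the arm-by-period term, and Protocol 2.0 expects implementation to vary by site, so τ = 0 is unlikely. Protocol 2.1.2 also expects most departments to exceed 100 prescriptions per month, where inflation is larger.

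The inputs are thin. The log-rate SD of 0.13 comes from three sites, with a 95% interval on 2 df of about 0.07 to 0.80. The mean of 940 per month is raised by one large site; the other two have about 600-650. This makes the size of the inflation uncertain but not its direction.

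Finally, silence is not a decision to ignore clustering: the site identifier is in the data, and Protocol 2.1.3 lets the plan be adjusted to the data. Neither commits to a cluster method, and the error structure of a primary analysis should not be chosen after the data are seen.

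**Conclusion.** The concern holds. As written, the Aim 1 model ignores the unit of randomisation, and its p-value and confidence interval for active versus passive cannot be relied on.

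- **Group term, as the plan words it:** about 10-31% false positives at 100 prescriptions per site-month and 26-70% at 620-940, with site SD 0.13 from the Table 1 counts.
- **Arm-by-period term, if that was intended:** about 5% with no site variation in change. With τ of 0.1 and 0.2 it is 7-8% and 13-17% at minimum volume, and 26-30% and 51-57% at about 940 per month.
- **Site-level t-test:** 3-6% throughout.

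These rates assume a two-sided 5% level, which the documents do not state, and the values of τ are assumptions.

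**What to change.** In Protocol 2.1.3 and SAP sections 1 and 6:

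1. State alpha and sidedness, and name the arm-by-period contrast as the Aim 1 estimate.
2. Specify a cluster-aware analysis. Either compute each site's pre-to-post log rate change and compare arms on a t distribution (8 − 2 = 6 df, or 5 with stratum, and one fewer in the seven-site set); or fit a Poisson or negative binomial mixed model in SAS GLIMMIX with a random site intercept, a random site-by-period effect and a small-sample correction of Kenward-Roger type. The degrees of freedom for the contrast must follow the number of sites, not site-months. Only the site-level t-test was checked by simulation here, so it is the safer primary choice.
3. Do not rely on an uncorrected sandwich variance with eight clusters, nor on an exact permutation test alone. Two-plus-two allocation in each of two strata gives 6×6 = 36 allocations, so the smallest two-sided p is 2/36 = 0.056.
4. Reconcile the stratum before using it as a covariate: SAP section 3 bases it on the percentage of prescriptions for patients aged 65 and over, section 6 on PIM prescribing level.

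The cost is wording and a little code, with no new data. Intervals will widen and power must be restated for the between-arm difference. For 7.1% versus 2.1% it stays at 99.8-100% with a relative site SD of 0.12-0.20. For an assumed 4.26% versus 3.55% (40% versus 50% reductions from 7.1%) it falls from 43% under independence to 14-21% at 1,200 post prescriptions per site.

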#### 2.1.4 Sample Size and Power Considerations (power calculated prior to trial) and Selection/Recruitment of Sites/Subjects

Power estimates are based on Aim 1, hypothesis 1 (i.e., primary outcome of change). The primary outcome is at the level of the individual prescribing decision. We plan to engage a total of eight VA sites with at least 1,200 eligible prescriptions per year to patients ages 65+ per ED. This will provide a total of approximately 4,800 eligible prescriptions during the pre-implementation period and 9,600 eligible prescriptions during the post time period. It can be reasonably assumed that these eligible prescriptions will be equally distributed between the randomization groups. Based upon preliminary data, we estimate that approximately 7.1% of these total prescriptions at baseline will be Beers PIMS. Given this sample size, we have near 100% power to detect a change in the risk of PIMs of 5% (i.e., 7.1% to 2.1%).

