## **Background, Purpose, and Significance**

### **1.1 Background**

Enhancing Quality of Prescribing Practices for Older Adults Discharged from the Emergency Department (EQUIPPED) is a multi-component program to reduce the prescribing of potentially inappropriate medications (PIMs) to older adults upon discharge from the Emergency Department (ED). It has three core components: 1) provider education, 2) Electronic Health Record (EHR)-based clinical decision support (CDS) including pharmacy quick order sets to facilitate provider order entry, and 3) provider audit and feedback with peer benchmarking. In order to inform a Veterans Affairs (VA) system-wide approach to improve prescribing safety for older Veterans, we will conduct a study to determine best practices for influencing provider prescribing behavior in order to decrease PIMs prescribed for older Veterans at the time of ED discharge. The overall goal of this project is to determine which EQUIPPED implementation strategy (active or passive feedback) is most effective to reduce prescribing of PIMs for older Veterans discharged from the ED.

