## **2.1 Aim 1 – Examining the Impact of Passive Provider Feedback vs. Active Provider Feedback**

### **2.1.2 Primary Implementation Science Trial Outcome – % of Prescriptions that Represent Potentially Inappropriate Medications (PIMs)**

The primary aim of the study is to compare the effectiveness of the EQUIPPED intervention to reduce the proportion of PIM prescriptions using active vs. passive processes for provider feedback aimed at improving prescribing toward older Veterans in the ED setting. PIMs will be defined according to the Beers criteria, which list medications that should generally be avoided in older adults. The Beers criteria have been used extensively in PIM research in the outpatient setting, along with data supporting the use of PIM measurement as an overall measure for better prescribing quality. Data on PIMs and all prescriptions will be gathered from the CDW from the eight VAMCs 6 months before and 12 months after the intervention period. As detailed in the power calculation, the study requires a minimum of 100 prescriptions per month

for older Veterans at each site. It is likely that most EDs will have many more than the required 100 prescriptions per month during the sampling period. The limit is above 100 because it is likely some EDs will have lower overall patient volumes, especially for older Veterans. Using our previously developed code (SQL) for the current EQUIPPED QI sites, we will be able to collect data needed to determine monthly PIM rates, number of older Veterans ( $\geq 65$  years of age) seen monthly, number of older Veterans who were discharged home, number of prescriptions for these discharged Veterans, and the number of PIMs, including specific drugs. For the sites, we will be able to describe the volume of ED visits overall and for older Veterans, the number of providers, and the number of overall prescriptions. We will ensure data validity by checking for inter-rater agreement on 10% of the data gathered by CDW and chart review at each site by the champions. **The primary endpoint will be the reduction in PIM risk from baseline to 12-months after the EQUIPPED Intervention, with a benchmark goal of <5% at each site.** We have data suggesting that PIM risks vary at sites from 7.4-11.8% at baseline (standard deviation of 0.8 to 1.9).

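### The near-100% power is credited to the active-versus-passive hypothesis but is power for one overall pre-post change; no superiority power for the arm contrast is given, and no calculation allows for 8 randomised sites

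*Protocol*

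**What the plan says.** Protocol 2.1.4 opens with "Power estimates are based on Aim 1, hypothesis 1 (i.e., primary outcome of change)". It plans eight sites with at least 1,200 eligible prescriptions a year each, giving about 4,800 before and 9,600 after implementation, and a 7.1% baseline. It concludes "Given this sample size, we have near 100% power to detect a change in the risk of PIMs of 5% (i.e., 7.1% to 2.1%)". SAP section 1 repeats this and calls the change absolute: "we have near 100% power to detect an absolute change in the risk of PIMs of 5% (i.e., 7.1% to 2.1%)".

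The only Aim 1 hypothesis, in Protocol 2.0 and again in the SAP introduction, is that "the decline in PIM rates will be greater in the presence of EQUIPPED with active feedback compared to EQUIPPED with passive feedback". The overall goal in Protocol 1.1 is to "determine which EQUIPPED implementation strategy (active or passive feedback) is most effective to reduce prescribing of PIMs".

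Other text points to a pre-post question. Protocol 2.1.2 (and SAP section 2) says "The primary endpoint will be the reduction in PIM risk from baseline to 12-months after the EQUIPPED Intervention". Protocol 2.1.3 (and SAP section 1) says "Our primary aim, on which we will base sample size, is the evaluation of the EQUIPPED implementation".

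Eight facilities are randomised, four per arm (Protocol 2.0; SAP section 3 for facility-level randomisation). The Aim 1 model handles the arms "by including randomization group as a variable in the model", and SAP section 6 adds stratum. SAP Table 2 gives prescriptions per group for non-inferiority of passive to active feedback.

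**The concern.** The power is credited to a hypothesis about the difference between two arms, yet no active rate, passive rate or arm difference enters it. The trial exists to choose between two feedback strategies. A reader who takes near 100% as the power for that choice would give too much weight to a null arm result and might conclude that the strategies are equivalent. The independent units for the arm comparison are eight sites, and neither document says how much power four against four provides for superiority.

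**Working it through.** **1. The plan's own figure.** Inputs from Protocol 2.1.4: 4,800 pre, 9,600 post, 7.1% to 2.1%.

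z = 0.05 / √(0.071×0.929/4,800 + 0.021×0.979/9,600) = 0.05 / 0.003985 = 12.5.

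Power is effectively 100%, so the figure reproduces as a pre-post comparison of independent prescriptions.

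**2. Does it survive clustering?** Use a one-sample t-test on 8 site-level changes (7 df, two-sided 5%). The SD of change is an assumption. For a 5-point drop, power is above 99.9% with SD 1.9 points and 99.3% with SD 2.7. Adding sampling error at 600 pre and 1,200 post prescriptions per site, variance 0.071×0.929/600 + 0.021×0.979/1,200 = 0.000127, the SD 2.7 case has noncentrality 0.05/√((0.027² + 0.000127)/8) = 4.83 and power about 98%.

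**3. SAP Table 2.** All 16 entries match 2×SD²×(1.645 + 0.842)²/margin² to within 2. For example, SD 1.0 and margin 0.10 give 1,237, as printed. This is a two-sample formula on independent observations with no site term. (These multipliers bear on the 85% power label, which is a separate matter.)

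**4. Power for the arm contrast.** The documents give no alpha, passive effect or between-site variation in change, so these are assumed: two-sided 5%; SD between sites of the true log change τ = 0.1, 0.2 or 0.3; passive cut 20%, with other values shown. From the documents: baseline 7.1%; active cut 40% (SAP Table 2) or nearly 50% (Protocol 1.3); n = 1,200 per site-year (the floor) or (7,756 + 7,164 + 18,868)/3 = 11,263 (mean of SAP Table 1).

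The contrast is the difference between arms in log change. Each arm has 2n pre and 4n post prescriptions:

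var = 2/(2n×0.071) + 1/(4n×pA) + 1/(4n×pP).

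With independent prescriptions, power = Φ(|log(pA/pP)|/√var − 1.96). With site as the unit, add 2τ²/4 to var and use the noncentral t with 5 df (8 sites, less 2 arms and 1 stratum term).

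Worked case, 40% versus 20%, n = 1,200: pA = 4.26%, pP = 5.68%, |log ratio| = 0.2877.
- var = 0.01174 + 0.00489 + 0.00367 = 0.0203, SE = 0.1425, independence power 52%. On the risk-difference scale, SE = 0.00864 for a gap of 0.0142, power 38%.
- τ = 0.2: var = 0.0203 + 0.02 = 0.0403, noncentrality = 0.2877/0.2007 = 1.43, critical t = 2.57, power 22%.

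| Active / passive cut | n per site-year | Independent (log scale) | By site, τ = 0.1 / 0.2 / 0.3 |
|---|---|---|---|
| 40% / 20% | 1,200 | 52% | 31 / 22 / 15% |
| 50% / 20% | 1,200 | 90% | 64 / 46 / 32% |
| 40% / 20% | 11,263 | about 100% | 77 / 35 / 19% |
| 50% / 20% | 11,263 | about 100% | 99 / 71 / 42% |
| 40% / none | 1,200 | 95% | 74 / 54 / 37% |
| 40% / 30% | 1,200 | 19% | 12 / 10 / 8% |

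At the floor volume, a 40% versus 20% contrast is far from near 100% even under independence. At Table 1 volumes sampling error matters little and τ largely decides the answer.

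**The case against.** The strongest defence is that the figure is nearly labelled for what it is. It is glossed as concerning change, the bolded endpoint is reduction from baseline, and the sample size is said to rest on evaluating implementation. That stands: this is a sound pre-post calculation with the wrong hypothesis attached, plus an omission for the arm comparison.

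The power was also calculated before the trial, so a later statement changes no design decision, and a site-level confidence interval would tell readers more about a null result. That is fair and limits the consequence, but it does not make the attribution right.

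The 1,200 is a floor, and both documents expect most sites to exceed 100 prescriptions a month. Hence the second volume in the table.

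Three stronger readings are tempting, and the documents do not support them:
- That near 100% is miscalculated or collapses under clustering. Steps 1 and 2 show otherwise.
- That the arms are never compared in any sizing. SAP Table 2 does compare them, for non-inferiority.
- That the trial is shown to be underpowered for active versus passive. The passive effect and τ are not given, and some cells of the table show high power. The standard deviation of 0.8 to 1.9 in Protocol 2.1.2 cannot settle this: the text does not say whether it describes sites, months or changes, so no range on the percentage-point scale is offered here.

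**Conclusion.** The concern holds in this form: the near-100% figure is valid for one overall pre-post change and is wrongly credited to the active-versus-passive hypothesis. Superiority power for that hypothesis is absent from both documents, and neither the main figure nor SAP Table 2 allows for randomising eight sites.

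The misattribution follows from the text alone. The size of the gap depends on the assumptions in step 4. With a 20% passive cut, site-level power runs from 15% (active cut 40%, 1,200 prescriptions, τ = 0.3) to 99% (active cut 50%, 11,263 prescriptions, τ = 0.1). That spread is the reason to report a range. This should be fixed, but the remedy is a labelling correction and a disclosure, and the design does not change.

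**What to change.** - **Protocol 2.1.4 and SAP section 1, existing figure:** keep it on record, label it as power for the overall pre-post change with prescriptions treated as independent, and remove its attribution to hypothesis 1.
- **Same sections, addition:** give a dated statement of the power, or the minimum detectable ratio of declines, for active versus passive with site as the unit, for the eight-site intention-to-treat set. State alpha, a range of active cuts (40% to 50%) and passive cuts, a range of between-site SD, and volumes from 1,200 up to those in SAP Table 1.
- **Protocol 2.1.3 and SAP section 1, model:** name the arm-by-period contrast, with site-level variation, as the Aim 1 arm comparison. As written, the model text names neither, so a new power statement would have no defined analysis to describe.

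The cost is a few sentences in two documents, one clarified model term and a less favourable figure for the arm comparison. No sites are added.
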